We expect to recruit 100 patients, we also expect patients will be equally distributed in the following 3 categories: receiving low (0-3), intermediate (4-6) and high (7+) CAT sessions due to the nature of each patient's random visits. Power analysis was done based on pairwised T-Test with these assumptions for simplicity. With 33 patients in each group, assuming 80% power and 0.017 significance level of alpha after Bonferroni ad justification of multiple comparisons, we will observe a minimum effect size of 0.813. This is to say that 80% of the Peds QL scores in the lower session CAT group will be below the average of scores in the higher session CAT group. Thus, what we would expect to see in the positive dose-response relationship.

We will also conduct subgroup analysis by age group if the sample size is large enough since Peds QL is designed by age group.

F. Summarize Knowledge to be Gained

Integrative and holistic therapies are being used throughout healthcare. We know that families are using alternative therapies without rigorous evidence documenting their worth. We therefore strive to build a body of literature showing evidence that CAT helps children with cancer feel better.

G. Appendices

- 1. PedsQL
- 2. Resilience Scale
- 3. Faces Scale
- 4. Inclinometer information
- 5. Patient/Family Survey

H. References:

- Bhat SR, et al. (2005) Profile of daily life in children with brain tumors: an assessment of health-related quality of life.[see comment]. *J Clin Oncol, 23,* 5493-5500.

10.4 Compliance with Trial Registration and Results Posting Requirements

Under the terms of the Food and Drug Administration Modernization Act (FDAMA) and the Food and Drug Administration Amendments Act of 2007 (FDAAA), as the Sponsor of this trial, this trial and its results are subject to the requirements for submission to the Clinical Trials Data Bank, and will be properly registered at http://www.clinicaltrials.gov. Information posted will allow subjects to identify potentially appropriate trials for their disease conditions and pursue participation by calling a central contact number for further information on appropriate trial locations and trial site contact information.

10.5 Quality Management System

By signing this protocol, the Sponsor-Investigator agrees to be responsible for implementing and maintaining a quality management system with written development procedures and to ensure that trials are conducted and data are generated, documented, and reported in compliance with the protocol, accepted standards of Good Clinical Practice, and all applicable federal, state, and local laws, rules and regulations relating to the conduct of the clinical trial.

The investigational site will provide direct access to all trial-related sites, source data/ documents, and reports for the purpose of monitoring and auditing by the DSMC audit team, and inspection by local and regulatory authorities.

10.6 Data Management

10.6.1 Monitoring and Oversight

The sponsor investigator will be responsible for monitoring the trial per the trial monitoring plan, in addition to overseeing the safety and efficacy of the trial including any specimens collected, executing the data and safety monitoring (DSM) plan, and complying with all reporting requirements to local and federal authorities. This oversight will be accomplished through additional oversight from the Data and Safety Monitoring Committee (DSMC) at the University of Colorado Cancer Center (CU Cancer Center). The DSMC is responsible for ensuring data quality and study participant safety for all clinical studies at the CU Cancer Center, which is the coordinating institution of this trial. A summary of the DSMC's activities is as follows:

- Conduct of internal audits
- Ongoing review of all serious adverse events (SAEs) and unanticipated problems (UAPs)
- May submit recommendations for corrective actions to the CU Cancer Center's Executive Committee

Per the CU Cancer Center Institutional DSM Plan, SAEs and UAPs are reported to the DSMC,

IRB and the sponsor investigator per protocol. All SAEs and UAPs are to be reported to the DSMC within 7 (for fatal or life-threatening events) or 15 (non-life-threatening events) calendar days of the sponsor investigator receiving notification of the occurrence.

Each subject's treatment outcomes will be discussed by the site PI and appropriate staff at regularly scheduled meetings. Data regarding number of subjects, significant toxicities, dose modifications, and treatment responses will be discussed.

The sponsor investigator will provide a DSM progress report to the CU Cancer Center DSMC on a recurring basis (either every six or twelve months based on DSMC vote). The DSM report will include a protocol summary, current enrollment numbers, summary of toxicity data to include specific SAEs, UAPs and AEs, any dose modifications, all protocol deviations, and protocol amendments. The DSM report submitted to the DSMC will also include, if applicable, the results of any efficacy data analysis conducted. Results and recommendations from the review of this progress report by the DSMC will then be provided to the sponsor investigator in a DSMC review letter. The sponsor investigator is then responsible for ensuring this letter is submitted to the site's IRB of record at the time of IRB continuing review.

10.6.2 Quality Control and Quality Assurance

Clinical site monitoring will be conducted to ensure that the rights and well-being of human participants are protected, that the reported trial data are accurate, complete, and verifiable, and that the conduct of the trial is in compliance with the currently approved protocol/ amendment(s), with GCP, and with applicable regulatory requirement(s).

Site monitoring visits will be performed by the CU Cancer Center Clinical Monitor on a regular basis, pursuant to the Clinical Monitoring Plan (CMP), incorporated herein by reference. The CMP describes in detail who will conduct the monitoring, at what frequency monitoring will be done, at what level of detail monitoring will be performed, and the distribution of the monitoring reports. During these visits, information recorded on the CRFs will be verified against source documents. Additional computer programs that identify selected protocol deviations, out-of-range data, and other data errors within the electronic data entry may also be used to help monitor the study. As necessary, requests for data clarification or correction will be sent to the PI.

> Independent audits will be conducted by the CU Cancer Center DSMC to ensure monitoring practices are performed consistently across all participating sites, if applicable, and that monitors are following the CMP. In addition, audits may be conducted at any time by appropriate regulatory authorities and/or the IRB.

10.7 Institutional Review Board

The protocol, informed consent form(s), recruitment materials, and all subject materials will be submitted to the Colorado Multiple Institutional Review Board (COMIRB) for review and approval. Approval of both the protocol and the consent form must be obtained before any subject is enrolled. Any amendment to the protocol will require review and approval by COMIRB before the changes are implemented to the study. All changes to the consent form will COMIRB approved; a determination will be made regarding whether previously consented participants need to be re-consented.

12.0 APPENDICES

12.1 ECOG Performance Status

| Grade | Description | |
|----------------------|--|--|
| 0 | Normal activity. Fully active, able to carry on all pre-disease | |
| V | performance without restriction. | |
| | Symptoms, but ambulatory. Restricted in physically strenuous | |
| 1 | activity, but ambulatory and able to carry out work of a light or | |
| | sedentary nature (e.g., light housework, office work). | |
| | In bed <50% of the time. Ambulatory and capable of all self-care, but | |
| 2 | unable to carry out any work activities. Up and about more than 50% | |
| | of waking hours. | |
| 3 | In bed >50% of the time. Capable of only limited self-care, confined | |
| 5 | to bed or chair more than 50% of waking hours. | |
| 1 | 100% bedridden. Completely disabled. Cannot carry on any self-care. | |
| 7 | Totally confined to bed or chair. | |
| 5 | Dead. | |
| | | |
| * As published in An | n. J. Clin. Oncol.: Oken, M.M., Creech, R.H., Tormey, D.C., Horton, J., Davis, T.E., | |
| McFadden, E.T., C | arbone, P.P.: Toxicity And Response Criteria Of The Eastern Cooperative Oncology | |
| Group. Am J Clin | Oncol 5:649-655, 1982. The Eastern Cooperative Oncology Group, Robert Comis | |
| M.D., Group Chair. | | |

12.2 Common Terminology Criteria for Adverse Events V4.0 (CTCAE)

The descriptions and grading scales found in the revised NCI Common Terminology Criteria for Adverse Events (CTCAE) version 4.0 will be utilized for adverse event reporting. (http://ctep.cancer.gov/reporting/ctc.html)

12.3 Response Evaluation Criteria in Solid Tumors (RECIST) 1.1 Criteria for Evaluating Response in Solid Tumors

RECIST version 1.1* will be used in this study for assessment of tumor response. While either CT or MRI may be utilized, as per RECIST 1.1, CT is the preferred imaging technique in this study.

* As published in the European Journal of Cancer:

E.A. Eisenhauer, P. Therasse, J. Bogaerts, L.H. Schwartz, D. Sargent, R. Ford, J. Dancey, S. Arbuck, S. Gwyther, M. Mooney, L. Rubinstein, L. Shankar, L. Dodd, R. Kaplan, D. Lacombe, J. Verweij. New response evaluation criteria in solid tumors: Revised RECIST guideline (version 1.1). Eur J Cancer. 2009 Jan;45(2):228-47.

Product: Pembrolizumab COMIRB 16-2300 Version Date: 6/17/2021 PI: [name]

12.4 Immune Response modification to Response Evaluation Criteria in Solid Tumors (irRECIST) for Evaluating Response in Solid Tumors

irRECIST* will also be used in this study for assessment of tumor response. While either CT or MRI may be utilized, as per irRECIST, CT is the preferred imaging technique in this study.

* As published in Clinical Cancer Research:

- Unidimensional measurements (longest diameter) have been shown to have less variability.
- PD thresholds for irRECIST and RECIST are aligned, allowing for comparisons to be made between trials and to historical data

12.4.1 Baseline Assessment Using irRECIST

Step 1. Identify the index target lesions (unidimensional, >/= 10mm, five lesions total, two lesions per organ).

Step 2. Add the sum of all target lesions.

12.4.2 Post-Baseline Assessments Using irRECIST

Step 1. Identify the index target lesions.

Step 2. Add the sum of all target lesions. New lesions are incorporated in the total tumor burden measurement.

Step 3. Assess response per criteria in table below.

Step 4. Wait up to 12 weeks to confirm PD to account for flare.

Product: Pembrolizumab COMIRB 16-2300 Version Date: 6/17/2021 PI: [name]

| | Response Criterion |
|--|--|
| Immune-mediated complete response (irCR) | Complete disappearance of all lesions (whether measurable or not, and no new lesions). |
| Immune-mediated partial response (irPR) | Decrease in tumor burden \geq 30% relative to baseline. |
| Immune-mediated stable disease (irSD) | Criteria for irCR, irPR, and irPD are not met; does not require confirmation. |
| Immune-mediated progressive disease (irPD) | Increase in tumor burden $\geq 20\%$ relative to nadir (minimum 5 mm) confirmed by a consecutive assessment ≥ 12 weeks from the date first documented. |

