3.2 Secondary Objectives

The secondary objectives for this study are:

- To characterize dose-limiting toxicities (DLTs), maximum tolerated dose (MTD), and recommended phase 2 dose (RP2D) for the combination.
- To assess other measures of anti-tumor activity of the combination of pembrolizumab and cabozantinib in subjects with locally advanced or metastatic renal cell carcinoma.
 - irRECIST (Immune-related response criteria) response
 - Progression-free survival
 - Overall survival
 - Time to progression of overall disease
 - Time to progression of bone metastasis or skeletal-related event
 - Clinical benefit rate [complete response (CR) + partial response (PR) + stable disease (SD)]
 - Duration of response or disease stability
 - Duration on treatment in subjects treated beyond progression

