5.2.1.2 Dose Modification (Escalation/Titration/Other)

Subjects will be monitored for AEs from the time of signing informed consent through 30 days after the date of the decision to permanently discontinue pembrolizumab and/or cabozantinib treatment.

Once the DLT assessment period has passed, pembrolizumab and/or cabozantinib may be held or dose modified independent of the other agent for adverse events attributed to one but not both drugs. The Principal Investigator should be notified when this occurs.

Dosing interruptions are permitted in the case of medical / surgical events or logistical reasons not related to study therapy (e.g., elective surgery, unrelated medical events, subject vacation, and/or holidays). Subjects should be placed back on study therapy within 3 weeks of the scheduled interruption, unless otherwise discussed with the Principal Investigator. The reason for interruption should be documented in the subject's study record.

Interruption of pembrolizumab and/or cabozantinib treatment for AEs may occur at any time per investigator discretion, if the investigator feels it is in the interest of the subject's safety and/or will optimize drug tolerability. If treatment is interrupted due to AEs for more than 6 weeks, discussion and approval from the Principal Investigator is required prior to resuming therapy.

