5.2.2 *Timing of Dose Administration*

Trial treatment should be administered on Day 1 of each cycle after all procedures/assessments have been completed as detailed on the Trial Schedule of Events Chart (Section 6.0). Trial treatment may be administered up to 3 days before or after the scheduled Day 1 of each cycle due to administrative reasons.

All trial treatments will be administered on an outpatient basis.

Pembrolizumab 200 mg will be administered as a 30 minute IV infusion every 3 weeks. Every effort should be made to target infusion timing to be as close to 30 minutes as possible. However, given the variability of infusion pumps from site to site, a window of -5 minutes and +10 minutes is permitted (i.e., infusion time is 30 minutes: $-5 \min/+10 \min$).

The Pharmacy Manual contains specific instructions for the preparation of the pembrolizumab infusion fluid and administration of infusion solution.

Cabozantinib will be obtained commercially. Subjects will be given oral and/or written instructions on dose to be taken by the investigator or by properly trained staff designee. Subjects will receive a medication diary with written dosing instructions and be asked to record the time and date they take each dose. Subjects will be instructed to bring their medication diary to each study visit for assessment of compliance.

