| Scheduling Window (Days): | -28 to -1 | | ± 3 | ± 3 | ± 3 | ± 3 | ± 3 | ± 3 | Within 30 days post treatment discontinuation | ±1 month |
| Tumor Imaging ^e (CT or MRI C/A/P +/- Whole Body Bone Scan ^d) | х | | | | X | | | х | | |
| RECIST 1.1 and irRECIST radiology read ^c | Х | | | | Х | | | Х | | |
| Archival Tumor Collection | Х | | | | | | | | | |
| Optional Fresh Tumor Biopsies (baseline and post-treatment) | Xe | | Xe | | | | | | | |
| • PD-L1 Testing | Х | | Х | | | | | | | |
| Immuno-Oncology Marker Testing | X | | X | | | | | | | |
| Correlative Studies | | | | | | | | | | |
| Bone Turnover Markers^g (in subjects with bone metastases only) | | Х | Х | | Х | | | X† | | |

^a Each treatment cycle = 3 weeks.

^b Urine pregnancy test is required only in women of childbearing potential.

^c CT or MRI CAP +/- bone scan and RECIST 1.1 assessments will be obtained at baseline and after every 3 cycles. irRECIST = immune-related response criteria. PET/CT is an acceptable alternative imaging modality. All scans can be performed \pm 7 days from the scheduled date.

d Whole Body Bone Scan is required for subjects with known or suspected bone metastases. All scans can be performed \pm 7 days from the scheduled date.

^e The baseline optional fresh tumor biopsy should be obtained during the screening period, prior to C1D1 treatment. The post-treatment optional fresh tumor biopsy should be obtained approximately 3-6 weeks (during cycle 2). Subjects may consent for separately for either baseline and/or post-treatment biopsies.

g Bone turnover markers may include β C-terminal telopeptide (β-CTX), bone specific alkaline phosphatase, and procollagen type 1 amino-terminal propeptide (P1NP). †Bone turnover markers will be collected through cycle 7 but not beyond. Bone tumor markers are not required during the second course of treatment.

ⁱ Total T3 = Total thriiodothyronine, Free T4= T4 (thyroxine) Free

^j Screening labs and pregnancy tests do not need to be repeated at C1D1 if done within 7 days of C1D1.

^k EKG tests will be performed through cycle 7, and then only as clinically indicated.

¹ In the absence of disease progression, pembrolizumab may be administered for up to 35 cycles (first course). If the patient progresses after discontinuing pembrolizumab, they may resume dosing for up to 17 additional cycles (second course), providing they meet criteria for retreatment. See protocol section 5.2.1 for additional information.

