8.2.3 Analysis of Anti-Tumor Activity

Descriptive statistics will be used to summarize all demographic and analytic data. Continuous data will be summarized using means, standard deviation, range, etc. Categorical data will be summarized using frequency tables.

Tumor response analyses will be based on definitions of responses according to both RECIST v1.1 and immune-related response criteria (irRECIST).

Objective response is defined as a complete or partial response, as determined by investigator assessment using RECIST and irRECIST. Subjects with missing or no response assessments will be classified as non-responders. For the primary objective, a one-sided exact binomial test will be used to assess whether the ORR is significantly greater than 20% in subjects taking a combination of pembrolizumab and cabozantinib.

Clinical benefit rate (CR + PR +SD) and duration will also be recorded.

Among subjects with an objective response, duration of response will be defined as the time from first occurrence of a documented objective response until the time of documented disease progression or death from any cause during the study, whichever occurs first. For all other subjects, duration of objective response will be censored at the day of the last tumor assessment.

Progression-free survival (PFS) will be defined as the time from study treatment initiation (Cycle 1, Day 1) to the first occurrence of documented disease progression or death from any cause during the study, whichever occurs first. For subjects who do not have documented progressive disease or death during the study, PFS will be censored at the day of the last tumor assessment.

Overall survival (OS) will be defined as the time from study treatment initiation (Cycle 1, Day 1) to death from any cause. For subjects who do not have documented death during or after the study, OS will be censored at the day of known survival status.

In subjects with bone metastases, time to progression of bone metastases or skeletal related event (SRE, defined as pathologic fracture, spinal cord compression, and radiation to bone or surgery to bone related to cancer) will also be recorded from Cycle 1 Day 1 to the time of progression or SRE.

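### Section 12.4.2 makes 12 weeks both the maximum and the minimum for confirming irRECIST progression, and the next on-schedule scan (7–11 weeks) cannot meet the irPD row

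*Combined protocol and SAP*

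**What the plan says.** Section 12.4.2 states the confirmation rule for immune-related progression twice.

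- Step 4 of the post-baseline procedure: "Wait up to 12 weeks to confirm PD to account for flare".
- The irPD row of the response table: an increase of at least 20% "relative to nadir (minimum 5 mm) confirmed by a consecutive assessment", with that assessment 12 weeks or more after progression was first documented. The row prints a greater-than-or-equal sign before the 12 weeks.

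The irSD row is the residual category: "Criteria for irCR, irPR, and irPD are not met; does not require confirmation".

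On imaging, footnote c of the Schedule of Events (Section 6.0) says that "assessments will be obtained at baseline and after every 3 cycles", with ±7 days on each scan; Section 7.1.2.5 agrees. A cycle is 3 weeks.

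Section 3.2 lists "irRECIST (Immune-related response criteria) response" among the secondary measures. Section 7.1.2.5 has both response and progression determined by RECIST 1.1 and by irRECIST, and Section 8.2.3 bases the tumor response analyses on both.

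Sections 5.6.2 and 5.7 refer to *confirmed* progression without giving an interval. Section 5.6.3 plans disease-status follow-up after treatment only for subjects who stop for a reason other than progression.

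**The concern.** One section sets the same 12 weeks as an upper limit and as a lower limit, and no other section says which governs. Two analysts given the same pair of scans 9 weeks apart, both showing progression, would reach different answers: confirmed under Step 4, not confirmed under the irPD row.

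The conflict matters in practice because of the imaging calendar. A rule that the next planned scan cannot satisfy leaves progression unconfirmed, and the table then supplies a favorable default, irSD. At stake are the irRECIST split between irPD and irSD and the irRECIST progression date. The clinical benefit rate is at stake only if it is computed by irRECIST, which the plan does not say.

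**Working it through.** The plan gives no figure of its own to reproduce; the check is interval arithmetic on its schedule.

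**Inputs.** Threshold: 12 × 7 = 84 days (Section 12.4.2). Cycle: 21 days (Section 6.0, footnote a). Scans: every 3 cycles, ±7 days each (Section 6.0, footnote c; Section 7.1.2.5).

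**Gap to the next on-schedule scan.** 3 × 21 = 63 days. With ±7 days on each of two scans: 63 ± 14 = 49 to 77 days, or 7 to 11 weeks.

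**Gap to the second following scan.** 2 × 63 = 126 days; 126 ± 14 = 112 to 140 days, or 16 to 20 weeks.

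| Confirming scan | Days from first progression | Step 4 (at most 84) | irPD row (at least 84) |
|---|---|---|---|
| Next | 49–77 | always met | never met |
| Second following | 112–140 | never met | met, if *consecutive* need not mean the very next scan |

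No on-schedule scan satisfies both rules.

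**When the next scan can reach 84 days.**

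- Visit drift. Section 5.2.2 says: "Trial treatment may be administered up to 3 days before or after the scheduled Day 1 of each cycle". If each of three Day 1 visits slips 3 days late, later cycles are re-anchored and both scan windows are used in full, the gap is 3 × 24 + 14 = 86 days. This is a corner of the allowed range.
- Interruption. For holds unrelated to study therapy, Section 5.2.1.2 says: "Subjects should be placed back on study therapy within 3 weeks of the scheduled interruption". If a 3-week hold shifts the scans with the cycles, the gap is 63 + 21 = 84 days nominal, or 70 to 98 with scan windows.
- Holds in general. Assume that scans move with cycles and that each scan falls independently and uniformly on a whole day within ±7, giving 15 × 15 = 225 pairs. The share of pairs reaching 84 days is then:

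| Delay between scans | Pairs reaching 84 days | Share |
|---|---|---|
| none | 0 | 0% |
| 1 week | 1 | 0.4% |
| 2 weeks | 36 | 16% |
| 3 weeks | 120 | 53% |
| 4 weeks | 197 | 88% |
| 6 weeks | 225 | 100% |

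**Where an unconfirmed progressor lands.** irPR is judged against baseline and irPD against nadir. After a nadir decrease of d, 20% regrowth leaves 1.2 × (1 − d) of baseline. This is still at or below 0.70 when d is at least 1 − 0.70/1.2 = 41.7%. A nadir of −60%, for example, becomes −52%, and that subject still meets irPR. Other unconfirmed progressors meet none of irCR, irPR and irPD, so they are irSD by definition.

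**Size per subject.** 1/38 = 2.6 percentage points of the planned Phase II evaluable total; 1/20 = 5.0 points if the trial stops after Stage I.

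**The case against.** The strongest reply is that the practical effect may be small, and much of that reply stands.

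- *Consecutive* is not defined. A subject treated beyond progression under Section 5.7 may be scanned again at 16–20 weeks and meet the irPD row with no delay at all. A reader might infer that 84 days can be reached only through delay or drift; that is wrong unless *consecutive* strictly means the next scan.
- Section 7.1 allows unscheduled procedures when clinically necessary. Section 5.2.1.2 also allows interruptions for adverse events, and requires Principal Investigator approval to resume only beyond 6 weeks. Either can yield a qualifying scan.
- A reader might infer that most progressors would become irSD. The documents do not support this: they do not say how many subjects will progress, stop at first progression, continue treatment or have delayed cycles.
- irPD versus irSD does not alter irCR + irPR. The plan names no irPD/irSD table, no irRECIST-based PFS and no irRECIST clinical benefit rate. In a best-response table, a subject with irSD before progression is already counted as irSD and would not move.
- The lower limit rests on one sign in a table read from PDF. If the source prints at most 12 weeks, the two rules agree and the next on-schedule scan always qualifies.

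Step 4 might also be read as loose advice to allow for flare, with the table as the formal definition. That removes the contradiction but not the mismatch with the schedule: the next on-schedule scan still fails the table. A subject who stops at first progression still has no planned later disease assessment.

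**Conclusion.** The point holds as a contradiction within Section 12.4.2 that the imaging schedule makes operational. As printed, the next on-schedule scan always satisfies one rule and never the other, and the irPD row sends unconfirmed progressors who no longer meet irPR to irSD.

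The total effect cannot be estimated. The per-subject shifts apply only to subjects whose classification actually differs between the two rules. The conclusion assumes that the sign is printed correctly and, for the 7–11 week range, that cycles and scans stay on schedule without accumulated drift.

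Its reach is limited to the irRECIST irPD/irSD classification and progression date, plus the clinical benefit rate if irRECIST is used for it. Nothing here bears on irRECIST objective response, RECIST 1.1 results or the Phase II decision rule. This should be corrected because a listed secondary measure has two incompatible rules, but it does not threaten the primary analysis.

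**What to change.** 1. Check the inequality sign in the irPD row against the source document.
2. Reconcile Step 4, the irPD row and the 9-week imaging schedule into one confirmation rule that scheduled scans can meet, and define *consecutive*. Check it against *confirmed* progression in Sections 5.6.2 and 5.7. The length of the window, and any consequence for treatment, are for the sponsor to decide.
3. For the irRECIST analysis only, report first-documented progression without a qualifying later scan as its own category, unconfirmed progression, and not as irSD by default.
4. State which criteria the clinical benefit rate uses.
5. Date and justify the change. The trial is open-label and under way: Section 5.2.1.3.2 already provides for patients past 35 cycles at the 20-OCT-2020 version.

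The cost is wording in Section 12.4.2, a line in Section 8.2.3 and a consistency check of Sections 5.6.2 and 5.7. No extra scans are needed if the rule is written to the existing calendar. The downside is that the irRECIST disease control figure may come out lower.
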